8.3.8 Home Use and Data Collection

After the patient is released from the hospital, the home use and data collection period starts. During this period, patients will be trained to control the BCI accurately, and data will be collected for research purposes. Between visits of the research team, patients are allowed to use the BCI system at any time they want for practice or real communication purposes (see [Section 8.3.13](#)). During phase 1 and 2, patients can train using the feedback given by the minidisplay/keypad. During phase 3 and 4, patients can also use the assistive technology device for practice between visits.

About six weeks after the patient was released from the hospital, one of the neurosurgeons or the nurse practitioner will visit the patient for a postsurgical medical checkup.

Raw data from the Activa PC+S is saved continuously (see [Section 8.3.11](#)) to monitor signal characteristics over time (see [Objectives Section 2](#)). A log book will be provided, and the caretakers will be asked to write down everything they consider relevant for the BCI project. Notably, this information will be anecdotal and subjective. It may contribute to the BCI optimization process, but research will not depend on it.

The research team will visit the patient on a regular basis ([Section 15.4](#)). During every visit, the VAS Mood and Motivation will be performed (in case of unreliable communication at the time of inclusion, VAS evaluations can only take place after the patient has reached adequate control with the UNP) and the functioning of the BCI system will be assessed using the information written down by the caretaker in the log, and by consultation of the caretaker and/ or patient. Also, a system checkup is performed using the clinician programmer. Subsequently, several tasks will be performed by the patient for training purposes. If necessary, system adjustments (on the level of feature selection, classification and/ or translation, see IMDD) will be made to optimize BCI performance ([Section 8](#); [Section 8.3.11](#); [Section 8.3.12](#)). In addition, psychological and signal data will be collected for research purposes ([Section 15.4](#)).

The number of visits, and the duration of each visit, will depend on the patient's condition and BCI performance. Initially, visits will be frequent, with a maximum of two per week. A maximum of 2 extra visits may be planned for training purposes only (no research data collection), in order to quickly familiarize the patient with the system, during the first, second or third week after release out of the hospital, depending on the postsurgical condition of the patient. After appropriate BCI control has been reached, frequency of visits will decrease ([Section 15.4](#)). Visits will be planned according to schedule, and in consultation with the patient and caretakers. If, during a scheduled visit, the required data cannot be obtained (completely) due to e.g. patient condition, time availability or motivation, the (remainder of) the data may be acquired during an extra visit scheduled shortly after the incomplete

session. The experimental time per visit, i.e. the time that the patient is actually performing tasks or tests, varies between 20 min and 198 min (3.3 h, only the last visit, [see Section 15.4](#) for an overview). The complete duration of a visit will be longer, however, because of pauses, set-up time, instruction time etc. The maximum presence of the research team at the patient's residence will be limited to 5 h per day.

The psychological wellbeing of the patient will be monitored by 1) close contact with the patient, 2) speaking with the caretakers, 3) monitoring of the VAS scores for mood&motivation and 4) the psychological questionnaires that are carried out on a regular basis. The VAS scores and psychological questionnaires will be monitored by a clinical neuropsychologist of the UMC Utrecht, and the researchers will report their observations to her as well. If the neuropsychologist feels that the psychological wellbeing of the patient is endangered, an intake will be scheduled to the outpatient center Affective and psychotic disorders of the UMC Utrecht.

In the case of unreliable communication, some of the tests can only be conducted if the patient can use the UNP system to communicate reliably.

8.3.9 BCI Training Procedure

Executive summary

The aim is to provide the user with one or more general purpose BCI switches, which is comparable to a switch we use with our hands. For the BCI switch to work the patient has to practice to get optimal results. Our experience with grid patients shows that the state of a patient is fundamental to the BCI performance. Based on this experience the training procedure is divided into three phases. The patient will 1) be familiarized with the system, 2) learn to use the switch in a number of training tasks and 3) learn to use the switch in combination with assistive technology. When the final phase is finished, the patient will be able to voluntarily control the assistive technology and use it for communication purposes. The procedure is further defined in this section.

Full description of procedures

General Training Procedure Overview

In the ideal case the patient will be provided with one or more switches that react instantly, are activated only when the patient wants it to, and are inactive otherwise. Using broadband high frequency (65 Hz to 95 Hz) power changes we can come close to the ideal switch as our research with epilepsy patients showed. However, this requires training for the patient and fine tuning of the system parameters related to feature selection, classification and / or translation (see IMDD). Further it is our aim to study the long term effects of using an intracranial BCI, which are unknown today. The end goal is that the patient can use the switch(es) unsupervised in combination with assistive technology to communicate by typing. For this the patient undergoes a four phase training procedure. During each phase the patient will gain more control over the device. The training will take place partly in the

hospital (depending on the length of stay of the patient) and at home (see Section 15.4). The duration of each phase depends on the patient's progress.

In the first phase the patient is familiarized with the concept of a BCI and controls for the first time a cursor on a screen using changes in brain activity. In the second phase the patient is trained to control the switch(es). The main objective is to decrease the time required to elicit a switch event and to increase the accuracy, i.e. increase the number of hits while decreasing the number of false positives. In the course of phase two, the level of proficiency is tested on a regular basis using a formal test. Once the patient succeeds in this test we conclude that he has a functional switch and has reached Level 1 Proficiency (supervised use, see Phase 2 Supervised BCI Control, below). In the third phase the patient is trained to increase the accuracy even more and to use the switch(es) to control assistive technology in a real life setting (unsupervised use, see Phase 3 Unsupervised BCI Control, below). The goal of phase 3 is to allow the patient to use the switch(es) independently of the researchers. The proficiency of the patient in doing so will be formally tested using a predefined sentence on a regular basis (Level 2 Proficiency). These data will be used to address the Primary Objective (see Section 2). In the last phase the patient is trained on autonomously switching the UNP system from 'stand-by' to 'on' mode and vice versa, without external help.

Frequency of visits by the research team will initially, during Phase 1 and 2, be maximally twice per week for at least 4 weeks, or until 28 weeks after implantation. During the first, second or third week only, depending on the condition of the patient, a maximum of 2 extra visits may be planned for training purposes, in order to quickly familiarize the patient with the system. Once a patient has entered phase 3, visits will initially occur once every 2 weeks, for 12 weeks. Subsequently, visits will occur once every 6 weeks until the end of the study. See Section 15.4A and B for examples of quick and slow scenario's. Notably, the actual scenario will depend on the individual patient's progress, and will probably be intermediate between the examples of Section 15.4. In addition, it may be necessary, when BCI performance suddenly decreases while being in a certain phase, to perform certain tasks from one of the previous phases. In that case, it will be made sure that the burden to the patient is not larger than originally planned.

Phase 1 - familiarization

The patient has two brain functions for controlling the device (control functions from here on) either by cognitive control and by motor imagery/attempt, or by different types of motor imagery/attempt. The function that showed the highest R^2 (as described in Section 8.3.7) is considered the primary control signal. The other function provides the secondary control signal. The patient will practice with both control signals. The patient is familiarized with controlling a computer with his thought (changes in brain activity). In this period a fine tuning of the device and the connected hardware is performed. These comprise the optimal frequency band or combination of frequency bands, the responsiveness of the system, i.e. how quickly a switch event is triggered, and the refractory period after a click, i.e. how quickly individual switch events can follow each other. Further the optimal threshold for eliciting a

switch event has to be identified. Phase 1 begins after the second surgery as soon as the patient's condition permits. Initially, the patient has to perform a 'Two Target Task'.

The Two Target Task is used extensively with the epilepsy grid patients. Training generally improves the performance over time and consequently patient confidence is increased. In this 1-dimensional two-target cursor control task the patient voluntarily modulates ECoG activity of the selected electrode pair in the specified frequency band to control the vertical movement of a cursor on a computer screen. The patient controls the cursor by engaging in the control function (to send the cursor up) or by relaxing (to send the cursor down). Each trial lasts 8.5 seconds and starts with an inter-trial interval (ITI) of 2.1 seconds, followed by the appearance of a target in the upper-right or lower-right corner of the computer screen (Target, vertical size 50% of screen height, horizontal size 10% of screen width). Next, a cursor appears (2.1 seconds after the target) and travels from left to right at a set pace (Cursor control, fixed travel-time of 2.3 seconds). The subject's task is to modulate the ECoG activity such that the cursor hits the target when it reaches the right edge. Correct hits are indicated by a color change of the target (Result); incorrect hits by an absence of color change.

[figure not shown]

Figure 5. Training phases

Phase 2 - supervised BCI control

In phase 2 the patient will learn to use the switch(es) quickly and reliably. Along with the patient learning how to interact with the system, the system has to be calibrated according to the user's needs. The sensitivity and specificity of the system have to be maximized. The system calibration has to be done for each control signal as the dynamics of the neuronal processes at the implantation sites differ. In addition, the mental strategy used by the patient and the specific needs of the patient will influence these values. The patient is trained on a 'Click Target Task'. He has to activate the switch in response to a target on a screen. Targets (blue rectangle at the center of the screen) are presented for a limited period (starting with 10 seconds, decreasing throughout the training). As soon as the patient elicits a switch event, the target turns green and disappears after 1 second. The patient is then presented with a fixation cross for 5 to 10 seconds. If the target is clicked away in time this is counted as a hit,

otherwise it is counted as a miss; if the patient activates the switch during the inter trial interval this is counted as a false alarm. Depending on the progression of the training, the Click Target Task will be performed using the primary and/or the secondary control signal.

Once a week (starting from week 2, 3 or 4, depending on the postsurgical condition of the patient), a formal testing takes place (Level 1 proficiency), in which the patient has to perform the 'Communication Channel Verification Questionnaire' where he has to answer 20 questions with obvious yes/no answers ([Section F1.3](#)). These questions have to be answered using the BCI. In addition, the answers need to be detected each within a maximum period of 30 seconds. Each answer is obtained as follows: following presentation of the question, there are two consecutive 30-sec periods in which a brain signal can be generated by the patient, one period representing 'yes', the other 'no' (random order, indicated on a computer screen). If the patient wants to answer 'yes', he activates his BCI switch during the 'yes' phase and keeps it deactivated during the 'no' phase. Thus, each question lasts two times 30 seconds, and the total task lasts maximally 25 minutes (including time to actually state the questions). When 80% of the questions were answered correctly (with 50% being chance level) on two occasions, the patient is considered to have achieved significant supervised BCI switch control. The 80% correct criterion is based on two sources of information:

- A published user questionnaire (Huggins et al., 2011), where 50% of ALS patients with mixed degree of paralysis stated that they would be satisfied with a BCI device that performs at least at 80% hit rate.
- The unwritten standard in EEG BCI that BCI control is achieved at and above 70% correct responses in a BCI task (Viduarre et al., 2010), which we want to exceed.

When both dlpc and motor strips are connected to the device, this process is first performed using the primary BCI control signal. The Research team may decide to repeat the phase two training procedure with the secondary control signal, or to switch to the secondary control signal if data suggest that this signal may yield better results. When two motor strips are connected to the device, supervised switch control may be investigated using several different electrode pairs and types of attempted movement. Training continues until the 'Communication Channel Verification Questionnaire' task criteria (a 80% score on two occasions/visits) are met with at least one of the control signals. Once the patient has achieved the set goal, phase 3 will start. We expect that reaching this first level of proficiency will take at least 4 weeks ([Section 15.4 for examples of a quick and slow scenario](#)). When the patient has not reached this level of proficiency within 28 weeks after implantation, the training will be discontinued and the patient will be excluded from further study ([see Section 8.4](#)).

Phase 3 - unsupervised BCI control

Once the patient is familiarized with the BCI control and can reliably control one or more basic switches in a supervised setting he starts the process of training to achieve unsupervised control of assistive technology. The focus will be on using the assistive technology device as a basic speller that the patient can use for communication. The

assistive technology the patient is equipped with (Touchy) provides the patient with scanning software. This software presents a keyboard on the screen; consecutively lines of letters are highlighted, when it is highlighted it can be selected by activating a single switch. Then the individual letters are highlighted for selection. By this method each letter of the alphabet can be selected by two activations of a single switch. The speed of the highlighting of the rows and columns depends on the speed the user can activate the switch with. Alternatively, if a patient had two strips over the sensorimotor cortex connected to the device and is able to control more than one switch reliably, the additional switch(es) can be used to increase speed of communication. A second switch can for example be used to change the direction of the highlighting (e.g. in case of a missed target), to quickly change to the next line, or for self-paced scanning (with highlighting of rows and columns each controlled with their own switch). When more than two switches can be controlled reliably, these may be used to for example move the highlighting up, down, left and right. During every visit, the patient will practice spelling using the scanning software.

The criterion for successful unsupervised BCI control ([see Primary Objective, Section 2](#)) will be if the system correctly detects a switch brain signal within 10 sec in a real-life cognitively engaging context, such as operating the abovementioned spelling device. The formal test is based on this criterion, and constitutes copying a 30 character sentence within 30 minutes, with a margin of maximally 20% faulty characters (Level 2 proficiency). Once a patient has entered phase 3 (after completion of phase 2, which we expect to occur between 4 and 28 weeks after implantation, [Section 15.4 for a schedule](#)), the patient is asked to copy this predefined sentence during every scheduled visit of the research team. Depending on the performance and condition of the patient the task may be terminated before the end of the sentence. Speed, number of letters spelled and number of errors is recorded. The task is recorded on video. On the basis of the results parameters of the BCI system can be adjusted to improve performance. Further, the patient will practice to produce his own sentences and to engage in a communication with the Research Team.

Once the patient has reached Level 2 proficiency, he has demonstrated that he can accurately control the BCI system using his brain signals. At this point, a possible request of the patient about using the UNP for environmental control (such as lights, television) will be considered by the research team. Conditions are that the device that will be controlled does not contain moving parts (e.g. door) and is not intended to generate temperature changes (e.g. electric blanket), and that the research team has approved the specific use and purpose.

Phase 4 – independent BCI control

The goal of phase 4 is to enable the patient to switch the UNP system from 'standby' to 'on' mode and vice versa without external help, through the generation of a key sequence with the switch. The standard mode of the system is the standby mode in which it does not react to the users command; this is to prevent false alarms. In this mode, however, the system does record and analyze brain activity. To activate the speller the patient has to produce a

specific pattern (key sequence) of switch events to unlock the system, similar to the pin code of a smartphone. The patient will be trained on generating this sequence using a Key Sequence Task. The sequence training is similar to the task used in phase 2. Here, the task however is more complex. The patient is again presented with a sequence of targets, but this time they are interleaved with non-targets. Targets and non-targets follow each other faster compared to the 'Click Target Task' with no interval between them in a fixed order. The patient has to activate the switch for the target and keep it deactivated for the non-targets. As soon as the patient can reliably produce the key sequence he can use the speller freely in the absence of the researcher. At this point the patient can make use of the UNP system to communicate with the researchers or care without any external help. The proficiency of switching the UNP system on and off will not be formally tested.

People involved

Research Team

Principal investigator

Responsibilities

The Research Team is responsible for BCI familiarization process.

The Research Team is responsible for administering the necessary tasks to fine-tune the switch parameters and choosing these parameters.

The Research Team is responsible for administering and evaluating 'Communication Channel Verification Questionnaire' task and the Copy Spelling Task of the predefined sentence to determine the level of BCI control.

The Principal investigator is responsible for the final decision regarding which BCI control channel to use as the primary channel.

8.3.10 Postsurgical Psychological Assessment

Executive summary

Throughout the study the patient has to perform 2 tests on a regular basis, to determine the quality of life of the patient, and how the quality of life is affected by the assistive technology. These tests will be performed during visits of the research team to the patient's home. The data are necessary to investigate secondary objective 1 (Section 2): to improve Quality of Life and user satisfaction. Additionally, during every visit the patient's motivation and mood is assessed using a VAS score.

In the case of unreliable communication at the time of inclusion, Quality of Life and user satisfaction questionnaires and mood and motivation assessment can only be conducted if the patient can use the UNP system to communicate reliably.

Full description of procedures

Throughout the study the patient has to perform 2 tests on a regular basis, to determine the quality of life of the patient, and how the quality of life is affected by the assistive technology. These tests will be performed during scheduled visits of the research team to the patient's

home (see Section 15.4). In addition, during every visit (e.g. those that are scheduled for BCI training and unscheduled visits for e.g. service to the system), the patient's motivation and mood is assessed using a VAS score. At the end of the study, the user satisfaction about the BCI device will be tested. All tests will be executed by a member of the research team.

Quality of Life

As part of addressing Secondary Objective 1 (Section 2), the quality of life will be assessed at the beginning (before implantation, see Section 8.3.1) and end of the study and four times in between in intervals of 12 weeks. The so called Anamnestic Comparative Self-Assessment (ACSA) will be used for this assessment, whose biographical +5 and -5 scale anchors the patient's memories of the best period in their life and their worst period ever. The test will take about 10 minutes to complete (Section F1.6).

The effects of the BCI on quality of life

As part of addressing Secondary Objective 1 (Section 2), the PIADS (Section F1.9) is used to estimate the effects of device on the quality of life. The test will be performed four weeks after the implantation and is repeated every 12 weeks until the end of the study.

PIADS (piads.net) is a 26-item, self-rating questionnaire that is designed to measure a person's perceptions of how assistive devices affect quality of life. The PIADS describes user experiences along three dimensions:

- Competence: Measures feelings of competence and usefulness.
- Adaptability: Signifies a willingness to try new things.
- Self-esteem: Indicates feelings of emotional wellbeing and happiness

Mood and Motivation

The mood and motivation of the patient will be assessed at the beginning of every visit (scheduled and unscheduled) using Visual Analogue Scales (Killgore 1999; Kleih et al., 2011, See Section F1.7). These data could be related to BCI performance, since this may be affected by mood and motivation.

User Satisfaction

As part of addressing Secondary Objective 1 (Section 2), user satisfaction will be measured during the last visit to the patient, using a dedicated questionnaire. The satisfaction with the BCI will be measured using a list of specific items, that will be rated by the patient on a four point scale that ranges from 'not satisfied at all' to 'very satisfied'. In addition, the opinion of the patient on the importance of each of these items will be assessed on a four point scale that ranges from 'not at all important' to 'very important' (See Section F1.8A+B).

People involved

Research team

Responsibilities

The research team will be responsible for planning and performing the tests.

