As part of addressing Secondary Objectives 1 and 2 ([Section 2](#)), the opinion of the patient about the importance of a range of aspects of the device will be determined using a dedicated questionnaire. The patient will rate each item on a four point scale that ranges from 'not at all important' to 'very important' ([See Section F1.8A](#)). This test will be repeated at the end of the study to monitor any changes. At that moment, the satisfaction of the patient about each of these issues will be measured too ([see Section F1.8B](#)).

In the case of unreliable communication at the time of inclusion, device questionnaires can only be conducted if the patient can use the UNP system to communicate reliably.

People involved

Neuropsychologist

Member of the Research Team

Responsibilities

The neuropsychologist is responsible for taking the presurgical psychological and neuropsychological tests and interpreting them. The member of the research team will be present for observation and help. The member of the research team will perform the postsurgical quality-of-life tests.

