8.6 Follow-up of subjects withdrawn from treatment

If patients are withdrawn from the study, their psychological wellbeing will be monitored as follows:

- 6 weeks and 12 weeks after withdrawal, the ADI-12 test (section F1.5) and Quality of Life test (ACSA, section F1.6) will be taken (only in the case of reliable communication)
- 12 weeks after withdrawal, we will schedule a concluding discussion with the caretakers and/or family.

The data obtained during these visits will be interpreted by the clinical neuropsychologist. If the neuropsychologist feels that the psychological wellbeing of the patient is endangered, an intake will be scheduled to the outpatient center Affective and psychotic disorders of the UMC Utrecht.

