10.2 Secondary study parameter(s)

Secondary study parameters are patient satisfaction and definition of a set of metrics for evaluation of efficacy of the BCI system for a larger clinical trial.

In the case of unreliable communication at the time of inclusion, secondary study parameters can only be investigated if the patient can use the UNP system to communicate reliably.

Patient satisfaction

This will be measured with standardized questionnaires and pattern of unsupervised use.

Quality of life

We assess the quality of life of the patient throughout the study. The so called Anamnestic Comparative Self-Assessment (ACSA) will be used for this assessment (Bruno et al., 2011), whose biographical +5 and -5 scale anchors the patient's memories of the best period in their life and their worst period ever. The first (presurgical) test serves as baseline measure. The test will be repeated five times after the implantation of the electrodes, in order to monitor whether quality of life changes over time ([See Sections 15.4 and 8.3.10](#)).

The effects of the BCI on quality of life

The PIADS ([Section F1.9](#)) is used to estimate the effects of device on the quality of life. PIADS (piads.net) is a 26-item, self-rating questionnaire that is designed to measure a person's perceptions of how assistive devices affect quality of life. For each of the 26 items, patients have to indicate (on a 7-point scale) whether this aspect of life has increased or decreased. The test will be performed four weeks after the implantation and is repeated every 12 weeks until the end of the study, in order to study changes over time.

Importance of Device Aspects and User Satisfaction

The opinion of the patient about the importance of a range of aspects of the device will be determined using a dedicated questionnaire. The patient will rate each item on a four point scale that ranges from 'not at all important' to 'very important' ([See Section F1.8A](#)). The test will be performed presurgically, and repeated at the end of the study to monitor any changes. At the end of the study, user satisfaction with the BCI will be measured using a list of specific items (the same items as in the 'Importance of Device Aspects questionnaire'), that will be rated by the patient on a four point scale that ranges from 'not satisfied at all' to 'very satisfied' ([See Section F1.8A+B](#)).

Pattern of Use

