15.4 Post Implantation Time Line

A. Example of a quick scenario, in which the patient reaches first level of proficiency within 4 weeks after implantation. In this case, the frequency of visits will decrease after 4 weeks, and Phase 3 and Phase 4 training will commence. Note that green and yellow columns are related to BCI performance by the patient, whereas purple, pink and blue are related to data collection for research purposes only. The planning of this research data collection is fixed and independent of the BCI training progress.

B. Example of a slow scenario, in which the patient reaches first level of proficiency just before the critical decision moment at 28 weeks after implantation, after which the frequency of visits will decrease and Phase 3 and Phase 4 training will commence. Note that green and yellow columns are related to BCI performance by the patient, whereas purple, pink and blue are related to data collection for research purposes only. The planning of this research data collection is fixed and independent of the BCI training progress (unless the patient is excluded from further study because of not reaching level 1 proficiency within 28 weeks after implantation, in that case, also data collection for research is terminated at that point).

A

B

Home Use and Data Collection Standard Operating Procedure

Executive summary

This Standard Operating Procedure (SOP) has been designed to support the research team of the UNP project in the safe and correct execution of the study protocol, part 'Home Use and Data Collection'. It describes the procedure during the research visits of members of the research team at the patient's home. If something is unclear, contact the study coordinator.

1. Consult patient and caretaker on functioning of the BCI system
2. Copy updates from the caretaker log
3. Press Patient Button on Streaming Unit to switch off
4. Take off antenna
5. Use the N'Vision Clinician Programmer to check battery level from Start Session screen (Fig 1): Log battery status and voltage

[figure not shown]

Figure 1

6. Use the N'Vision Clinician Programmer to check impedance as follows:
 - 6.1. Access the Measurement menu and select Electrode Impedance.

6.2. Select the Left (hemisphere) tab or the Right (hemisphere) tab (Fig 2).

6.3. Select the Settings button (Fig 3).

[figure not shown]

Figure 2

6.4. Select 0.25V amplitude value from the drop-down list.

6.5. Select Bipolar as electrode configuration option.

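### The device satisfaction rating is scheduled only at the last visit, so participants excluded at week 28 for missing Level 1 have no scheduled rating, and missingness depends on BCI failure

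*Combined protocol and SAP*

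**What the plan says.** **Timing of the rating.** Section 8.3.10 (User Satisfaction) says that "user satisfaction will be measured during the last visit to the patient", and its procedures paragraph says "At the end of the study, the user satisfaction about the BCI device will be tested". Section 10.2 agrees: "At the end of the study, user satisfaction with the BCI will be measured using a list of specific items". Before surgery only the importance of device aspects is rated. Section 8.3.1 repeats that form at the end of the study and adds: "At that moment, the satisfaction of the patient about each of these issues will be measured too". F1.8B is thus a single post-implant measurement.

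**The 28-week rule.** Under Section 8.3.9, repeated in 10.1, if Level 1 (supervised yes/no control, 80% correct on two occasions) is not reached within 28 weeks of implantation, "the training will be discontinued and the patient will be excluded from further study". The caption to the slow scenario in Section 15.4 says of such a participant: "in that case, also data collection for research is terminated at that point". Section 8.3.8 counts psychological data among the data collected for research.

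**After withdrawal.** Section 8.6 provides that "6 weeks and 12 weeks after withdrawal, the ADI-12 test (section F1.5) and Quality of Life test (ACSA, section F1.6) will be taken", where communication is reliable, followed by a closing discussion with caretakers or family at 12 weeks. F1.8 is not listed.

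**Related provisions.** Section 8.5 allows no replacement after the first implant surgery. Section 10.2 has no rule for a missing rating. Section 2 plans to choose evaluation indices for the larger trial from the relation of early performance to satisfaction and quality of life.

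**The concern.** Read together, these provisions leave a participant excluded at week 28 with no scheduled satisfaction rating. The cause of exclusion is failure to gain basic control of the device, so whether a rating exists depends on the outcome it is meant to be related to.

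Two uses of the data are affected. The first is the account of user satisfaction under secondary objective 1, which is likely to look more favourable if those with the poorest control are not asked. The second is the choice of indices for the larger trial. If performance is to be related to satisfaction, the lowest-performance participants are the most informative about where satisfaction is lost, and they would contribute no F1.8 rating. With five participants and no replacement after implant, each lost rating is one fifth of the data.

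**Working it through.** The plan states no figure on this point, so there is none to reproduce. The check has three parts.

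**1. Who is rated on the schedule as written**

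| Participant | Stays past week 28? | F1.8B scheduled? |
|---|---|---|
| Reaches Level 2 | yes | yes, last visit |
| Reaches Level 1, never Level 2 | yes | yes, last visit |
| Misses Level 1 by week 28 | no; research collection stops | none stated |
| Unreliable communication at inclusion and BCI does not work | no | not possible (8.3.10, 10.2) |

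The filter is Level 1. Study success is defined at Level 2 (Sections 8.1.1 and 10.1), so the rated group is wider than the successes.

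To show how much wider, assume a Level 1 rate of 6/7. This is borrowed from Section 6.3, where six of seven epilepsy patients exceeded 80% on a different task. Take the 50% Level 2 rate from Section 4.4, and assume that everyone at Level 1 stays to be rated. The share of end-of-study respondents not at Level 2 is then (6/7 − 1/2) / (6/7) = 0.42. For Level 1 rates from 50% to 100% the share runs from 0 to 50%.

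**2. What else exists for a participant excluded at week 28**

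- PIADS: first at week 4, then every 12 weeks (8.3.10), so weeks 4, 16 and 28. Two assessments precede the exclusion and a third coincides with it.
- ACSA: at baseline, at 12-week intervals, and again 6 and 12 weeks after withdrawal.
- Mood and motivation scales: at every visit.
- Use logs: continuous (8.3.11).

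The questionnaires and scales require reliable communication; the logs do not. None of these records satisfaction with the listed device aspects. Only F1.8 is missing altogether.

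**3. How likely a missing rating is**

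Inputs: n = 5 (Section 4.4) and a Level 1 failure rate f. The documents do not give f, so it is assumed. Treating participants as independent, P(at least one missing) = 1 − (1 − f)^5, and the expected number missing is 5f.

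| Assumed f | 1 − (1 − f)^5 | Expected missing of 5 |
|---|---|---|
| 10% | 1 − 0.9^5 = 0.41 | 0.5 |
| 1/7 (14%) | 1 − (6/7)^5 = 0.54 | 0.7 |
| 20% | 1 − 0.8^5 = 0.67 | 1.0 |
| 30% | 1 − 0.7^5 = 0.83 | 1.5 |

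The 50% in Section 4.4 concerns Level 2 and is not used as a Level 1 failure rate.

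**The case against.** **The last visit may include the withdrawal visit.** Section 8.3.10 words the timing per patient. Section 8.3.15 treats insufficient proficiency at week 28 as one way in which participation ends. Section 8.6 is framed as monitoring of wellbeing after withdrawal and does not address the withdrawal visit itself. The visit-by-visit charts in 15.4 could not be read in the text available. This part stands: the loss is not certain.

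The other reading is still the more natural one. Section 8.3.8 uses the term for one particular visit, the longest in the 15.4 schedule (198 minutes of task time). Section 10.2 speaks of the end of the study, which Section 12.5 defines as the last research data collection from the last patient. No readable text schedules a rating for a withdrawn participant. A clarifying sentence is needed on either reading.

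**Stronger readings that the documents do not support.**

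- A reader might infer that satisfaction would be known only for participants in whom the BCI succeeded. Those at Level 1 who never reach Level 2 miss the primary objective, yet remain and are rated.
- A reader might infer that nothing on satisfaction or quality of life would exist for those excluded. Section 8.1.2 defines patient satisfaction to include hours of use and quality of life, and the PIADS, ACSA and log data above cover part of that.
- A reader might infer a biased pooled estimate. Section 10 makes the analysis descriptive and per subject; no mean satisfaction is planned, and a missing form among five would be visible. That limits the harm, but there is still nothing to describe for the participant concerned.

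**The form may fit these participants poorly.** In phases 1 and 2 they have only keypad feedback for home practice and have not used the speller at home. Some items may not apply. F1.8 was not available to judge this.

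**Conclusion.** The concern holds in a limited form. As most naturally read, the plan obtains F1.8 satisfaction ratings only from participants who reached Level 1, so missingness depends on BCI failure and the lowest-performance end of the performance–satisfaction relationship has no F1.8 data. At an assumed Level 1 failure rate of 10% to 30%, the chance that at least one of five participants lacks a rating is 41% to 83%, with 0.5 to 1.5 missing on average.

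This rests on three assumptions: the failure rate, which the documents do not supply; independence between participants; and the reading that the last visit is the scheduled final visit. That those excluded would be less satisfied is plausible but not shown, so a favourable tilt is likely, not certain. No hypothesis test or primary endpoint is affected. The change is still worth making because it closes an outcome-dependent gap in a stated secondary objective with very little effort.

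**What to change.** State in Sections 8.3.10, 8.6, 10.2 and 15.4 that F1.8A+B is given at the withdrawal visit, or at the 6-week post-withdrawal visit already planned, to any participant with a reliable communication channel. Provide a not-applicable response for items about functions the participant never used. PIADS needs no extra administration, as it already falls due at week 28.

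In Section 10.2, report the ratings individually by proficiency level reached, with the number rated out of all implanted participants and the reason for each missing rating.

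The cost is one short form at an existing contact, which is a small added burden for someone likely to be disappointed. It cannot recover ratings from participants who have no reliable channel and for whom the BCI did not work; these should be reported as missing for that reason.
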